5.7 Recovery and Discharge

The subject will be recovered from the treatment and discharged from the hospital as per standard practices.

At 7 Days Post-Randomization or Discharge the following will be completed by a dedicated, pre-specified Blinded Study Stroke team member not involved in the patient's treatment: neurological exams (including NIHSS, mRS, and GOS), a review of any adverse events, and a review of current medications.

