5.9 Follow-Up Examination

5.9.1 Clinical

Several clinical outcome measures were selected for this study. These were chosen on the basis of their reliability, familiarity to the neurologic community, adaptability for use in

patients who have had a stroke, and comparability to end points used in other trials of thrombolytic therapy. The modified Rankin Scale (mRS) is an overall assessment of global handicap. In the original Rankin Scale, a score of zero indicates the absence of symptoms and a score of 5, severe disability. The modified Rankin Scale adds a score of 6 for fatal outcomes. The Glasgow Outcome Scale (GOS) is a global assessment of function.[42] A score of zero on the GOS indicates a good recovery; a score of 2 moderate disability; a score of 3 severe disability; a score of 4 survival but in a vegetative state; and a score of 5, death. It has been used in previous trials assessing outcome in hemorrhagic and ischemic stroke patients. [43][43] [43] [43] [43] [43] [43] [42] [42] [38] [36][36, 35] The National Institutes of Health Stroke Scale (NIHSS) is a 42 point scale that quantifies neurologic deficits in 11 categories. Normal function without neurologic deficit is given a score of zero.

Additionally a quality of life scale outcome measure will be utilized in this study. Quality of life scales are designed to be sensitive to changes in outcome from mild and moderate stroke undetected by other outcome measures. Important parameters not fully interrogated by conventional outcome scales can be assessed by quality of life scales, including emotion, communication, cognition, and social role function. Standard measures, such as the mRS, primarily evaluate physical aspects of stroke outcome, not addressing more relevant quality of life measures. The Stroke Impact Scale (SIS) is a validated assessment of quality of life specifically in patients with stroke. [44] [39] [37][37, 36]

All 24hr Post-Randomization (mRS, GOS, NIHSS), Day 7/Discharge (mRS, GOS, NIHSS), Day 30 (mRS, GOS, NIHSS), and Day 90 (mRS, GOS, NIHSS, SIS) clinical outcome measures will be assessed by a dedicated, pre-specified Blinded Study Stroke team member with NIHSS certification and expertise with a back up person named for cases in which the blinded team member was involved in the case during the acute hospitalization. Nursing staff, patients, and their family members will be instructed not to unblind the investigators performing these assessments.

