5.9.3 Serious Adverse Events

All serious adverse events (SAE's) occurring during the 90 days of study participation will be recorded. Adverse events and serious adverse events are critical endpoints and will be assessed as they occur and at the scheduled clinic visits. A serious adverse event is one that is fatal or life-threatening, is permanently or substantially disabling, requires or prolongs hospitalization, or any event that the treating clinician judges to be a significant hazard, contraindication, side effect, or precaution. For each recorded adverse event, the patient's attending physician will be asked to classify the causal relationship of the event to the study treatment as definitely related, probably related, possibly related, unlikely related, or not related. Especially detailed form and narrative reports of the following specific adverse events will be obtained:

- Neurologic Deterioration: Increase of 4 or more points in the NIHSS
- Symptomatic Hemorrhagic Event: an ECASS defined ICH visualized on follow-up imaging study and associated with a 4 or more point worsening on the NIHSS score*
- Angiographic or thrombectomy procedural complications: Groin hematoma requiring transfusion or surgery, vessel dissection, vessel perforation, presence of emboli in a previously uninvolved territory, or other unanticipated procedure-related event, device fracture
- Malignant cerebral edema: Edema associated with neurologic impairment or requiring medical or surgical intervention
- Subarachnoid Hemorrhage (SAH): Both symptomatic and asymptomatic SAH visualized on follow-up imaging study.

*Asymptomatic hemorrhage events are not considered serious adverse events

An unblinded Safety Monitor will review all serious adverse events individually on a continuous basis as they occur and aggregate unblinded data on adverse events quarterly. This individual will report independently to the appointed DSMB at regularly scheduled DSMB meetings. This individual also has the authority to alert the DSMB at any time if a potential safety issue arises. If at any point, these reviews raise any safety concerns, the DSMB will be empowered to suggest that the trial be placed on hold and request additional analyses of the trial dataset.

6. Study Primary Endpoints

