7.6 Blinding

This study is not blinded. Blinding is difficult, if not impossible, from a clinical perspective. It is not possible to blind the Investigator who treats the patient, nor is it possible to blind the internal review committee (IRC) members. Additionally, physicians treating subjects who experience an adverse event after must know how the stroke was treated in order to effectively report the adverse event and plan further treatment. Blinding the study is not required for interpretation of study outcomes. However to avoid bias in study results, the person performing the primary outcome assessment at 90 days

must be blinded to the subject's treatment assignment and have not been associated with the care of the subject during the acute treatment phase.

8. Study Withdrawal

Subjects may be terminated or withdrawn from the study for the following reasons:

- Voluntary withdrawal of consent— meaning that a subject voluntarily chooses not to participate further in the study. All data collected up to the withdrawal of consent will be maintained in the study database.
- Lost to follow-up — defined as a subject who is more than one month late to a study visit and for whom 5 documented telephone attempts to contact the subject and at least one certified letter were unsuccessful.
- Subjects may also be withdrawn at the investigator's discretion if within their best interest.

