15.3 Security, Privacy, and Confidentiality

VUMC employs several layers of data protection to ensure data security. The first part of security is physical protection of the hardware systems, access to which is limited to authorized personnel. By limiting access, ensuring only authorized personnel have access, and tracking all entry, we can ensure this risk is minimal. Additionally, REDCap has a built-in audit trail that tracks all user activity and changes made to the data entry fields with a date-time stamp.

16. Adverse Events

Adverse events (AE’s) may occur at any time after randomization. Pre-existing conditions (existing prior to randomization) will be documented in the subject’s medical record as part of prior medical history but will not count as an AE unless it worsens during the study. Adverse events (serious and non-serious) will be documented on an Adverse Event form. Non-serious adverse events will be recorded from randomization through hospital discharge or 7 days post-randomization (whichever is earlier). Serious adverse events will be recorded from randomization through the end of study (i.e., 90 day post-randomization follow-up).

Investigators will record characteristics of each adverse event on an Adverse Event form. Each adverse event will be judged by the Investigator as to its level of relatedness to the investigational devices and investigational procedure. In addition, the Investigator will identify the date of onset, severity and duration. Severity will be judged using the scale noted in Table 10. All adverse events will be monitored until they are adequately resolved or explained or until the subject reaches the end of the study.

Table 10. Definition of event severity for judgment by Investigator.

Term	Definition
Mild	Patient is aware of a sign or symptom, but that sign or symptom does not interfere with normal activity or symptom is both transient and resolved
Moderate	Symptoms interfere with the subject’s usual activity or symptoms require treatment
Severe	Symptom(s) cause either severe discomfort or have a significant impact of the subject’s usual activity and symptoms require treatment

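### Section 5.7 has the blinded assessor review adverse events at Day 7/discharge, which can unmask a minority of thrombectomy patients before the later mRS scores

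*Combined protocol and SAP*

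**What the plan says.** Section 5.7 lists the Day 7/discharge tasks and says that they "will be completed by a dedicated, pre-specified Blinded Study Stroke team member not involved in the" treatment of the patient. The tasks are "neurological exams (including NIHSS, mRS, and GOS), a review of any adverse events, and a review of current medications".

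Section 5.9.1 covers the 24-hour, Day 7/discharge, Day 30 and Day 90 visits: the "clinical outcome measures will be assessed by a dedicated, pre-specified Blinded Study Stroke team member with NIHSS certification". It provides two safeguards. One is a substitute assessor, "with a back up person named for cases in which the blinded team member was involved in the case during the acute hospitalization". The other is an instruction to those around the patient: "Nursing staff, patients, and their family members will be instructed not to unblind the investigators performing these assessments".

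Section 5.9.3 asks for detailed reports of particular events, among them "Angiographic or thrombectomy procedural complications: Groin hematoma requiring transfusion or surgery, vessel dissection, vessel perforation", new-territory emboli and device fracture. Section 16 adds that "Each adverse event will be judged by the Investigator as to its level of relatedness to the investigational devices and investigational procedure". It also has non-serious events recorded from randomization up to discharge or Day 7, so the section 5.7 visit falls at the end of that recording period.

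In Table 1, note 5 (blinded assessor) is attached to the mRS, NIHSS and GOS rows. It is not attached to the adverse-event or concomitant-medication rows. Note 3 limits the angiogram and the procedure to the thrombectomy arm.

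Section 7.6 states that the study is not blinded, but sets a rule for one person: "However to avoid bias in study results, the person performing the primary outcome assessment at 90 days" must be blinded to assignment and must not have taken part in the acute care. Section 7.3 scores deaths as mRS 6 and otherwise replaces a missing 90-day mRS with the latest score available.

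**The concern.** Treatment is open, so the primary endpoint depends on the person who scores the mRS not knowing the allocation. Section 5.7 gives that person a task that can disclose it. A patient with a groin hematoma that needed transfusion, or with a vessel perforation or a device fracture, has very probably been to the angiography suite, and under the protocol only the thrombectomy arm goes there. An assessor who has read such a record at Day 7 still knows it at Day 30 and Day 90.

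The mRS involves judgement between adjacent grades. If knowledge of the arm moves some scores, the ordinal odds ratio is biased, and the bias cannot be removed afterwards. The task also serves no purpose that requires a blinded person, because the schedule of events does not ask for one on those rows.

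**Working it through.** **1. Does the text create the exposure?**

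| Question | Where | Answer |
|---|---|---|
| Who reviews adverse events at Day 7/discharge? | 5.7 | The blinded assessor |
| Who scores mRS at Days 30 and 90? | 5.9.1 | The same dedicated role |
| Can the records identify the arm? | 5.9.3; Table 1 note 3 | Yes, for procedure-specific events |
| Does the back-up rule cover it? | 5.9.1 | No: its trigger is involvement in the case during the acute stay, and 5.7 describes its reviewer as not involved in treatment |
| Does the instruction not to unblind cover it? | 5.9.1 | No: it addresses nurses, patients and families, not records |
| Does the schedule require a blinded reviewer of events? | Table 1 note 5 | No |

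The exposure follows from the text.

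**2. How many patients?** The documents give no rate for recognisable procedural events. The nearest figure is the approximate 3% angiography risk in section 2.1. It includes contrast allergy and kidney dysfunction, which do not identify the arm, and omits groin hematoma. With 200 patients randomized 1:1, the thrombectomy arm has about 100. I assume that a fraction f of 3% to 10% is identifiable:

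- 100 × 0.03 = 3 patients
- 100 × 0.10 = 10 patients

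**3. Carried-forward scores.** Section 7.1 allows 10% loss: 200 × 0.10 = 20 patients, or about 10 per arm if loss is equal. Of those 10, 0.3 to 1 would be identifiable (10 × 0.03; 10 × 0.10). A Day 7 score is used only when no later score exists, so this route adds little.

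**4. Effect on the primary analysis.** The plan states no figure to reproduce here. Assumptions:

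- The true odds ratio is 1.0, with 100 patients per arm.
- mRS 0 to 6 is distributed 4/8/13/17/18/10/30%. This matches the roughly 25% good outcome and 30% mortality for untreated occlusion in section 1 (4 + 8 + 13 = 25; deaths 30).
- A fraction q of thrombectomy survivors with mRS 1 to 5 is scored one grade better.
- q = f × m, where m is the share of identifiable patients who are upgraded. I take m = 0.30.

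This gives q = 0.03 × 0.30 = 0.009 and q = 0.10 × 0.30 = 0.03.

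With 5 and 6 collapsed, as in section 7.2, the control proportions are 0.04, 0.08, 0.13, 0.17, 0.18 and 0.40. At q = 0.03 the thrombectomy proportions become 0.0424, 0.0815, 0.1312, 0.1703, 0.1776 and 0.3970. For example, mRS 0 is 0.04 + 0.03 × 0.08 = 0.0424.

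The log odds ratio comes from a large-sample proportional-odds fit without covariates. Its standard error is √[12 / (N(1 − Σp³))]. Here Σp³ = 0.0775, so SE = √[12 / (200 × 0.9225)] = 0.255. The false-favourable probability is Φ(log OR / SE − 1.96).

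| q | Meaning | log OR | OR | False-favourable |
|---|---|---|---|---|
| 0 | no misrating | 0 | 1.00 | 2.5% |
| 0.009 | 3% identifiable, 30% upgraded | 0.0061 | 1.01 | Φ(0.024 − 1.96) = 2.6% |
| 0.03 | 10% identifiable, 30% upgraded | 0.0204 | 1.02 | Φ(0.080 − 1.96) = 3.0% |
| 0.10 | 10% identifiable, all upgraded | 0.0678 | 1.07 | Φ(0.266 − 1.96) = 4.5% |

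A simulated Wilcoxon test with 100 per arm gave the same rates to within 0.1 percentage point.

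**The case against.** The strongest reply is that the review tells the assessor nothing about most patients. A thrombectomy patient with no procedural event looks like a control patient. This stands, and it sets the size of the point. A reader might infer that section 5.7 discloses the arm of every thrombectomy patient; the documents do not support that. Nor do they support assuming that 20% or 30% of all survivors are misrated (odds ratio about 1.14 or 1.22, false-favourable about 7.6% or 12.2%). That would need at least 20% to 30% of them to be unmasked through adverse-event records.

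Four further objections hold in whole or in part:

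- **Medications.** One might think that the medication review reveals the arm. Section 5.7 concerns current drugs, and section 5.6 standardizes management in both arms, including aspirin for seven days. Drugs given during the procedure would not normally be current at Day 7. Table 2 lists IV heparin after the procedure, which is at most an occasional clue.
- **Section 7.6 against 5.9.1.** One might read these as contradictory because 7.6 mentions only the 90-day assessor. They are compatible: 7.6 sets a rule for the primary assessment, and 5.9.1 and Table 1 extend blinding to the other visits. Section 7.6 would in fact disqualify an unmasked assessor; what is missing is a step that acts on this. Its remark about needing to know the treatment concerns physicians treating an adverse event, not the assessor.
- **Relatedness rating.** Sections 5.9.3 and 16 give this rating to the attending physician and the investigator. Section 5.7 does not say that the assessor sees it.
- **Same person.** The text fixes a role, not one individual per patient. That the Day 7 and Day 90 scorer are the same person is the natural reading of a dedicated, pre-specified assessor, but it is a reading.

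The direction is also uncertain. The identifying events are complications, and an assessor might score such patients worse rather than better. The calculation takes the direction that favours thrombectomy.

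**Conclusion.** The point holds in a limited form. Section 5.7 gives the blinded assessor a task that can unmask some thrombectomy patients before the Day 30 and Day 90 mRS. No passage shields the assessor from those records or calls in the back-up once it has happened.

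The likely effect on the primary result is small: an apparent odds ratio of about 1.01 to 1.02, and a false-favourable rate of about 2.6% to 3.0% instead of 2.5%. This rests on an assumed 3% to 10% identifiable, 30% of those upgraded by one grade, and the assumed mRS distribution. An odds ratio of 1.07 with a rate of about 4.5% is an upper illustration. The true rates of unmasking and of misrating are unknown. No sample size, power or alpha figure changes. This is an inexpensive improvement worth making because unmasking cannot be undone; it is not a flaw that undermines the trial.

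**What to change.** - In section 5.7, limit the blinded assessor to NIHSS, mRS and GOS. Assign the adverse-event and medication review to the unblinded investigator or the study coordinator. This brings 5.7 into line with Table 1 note 5.
- Give the blinded assessor's REDCap role no access to the adverse-event and procedure forms.
- In section 5.9.1, add unmasking as a trigger for the back-up: record when an assessor learns the allocation, and have the already named back-up score that patient's later visits.

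The cost is a wording change in two sections and one permission setting. No new staff are needed, because section 16 already has the investigator judge each event and section 13 already recommends a coordinator. The downside is two short contacts at the Day 7/discharge visit instead of one.

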5.8 Hospital Costs

For each subject, device costs (the market price for each device) will be collected for the hospitalization during which the index procedure took place. These costs will include device costs, materials used to treat the occlusion, and number of days spent in the hospital (ICU and non-ICU length of stay).

5.9 Follow-Up Examination

5.9.1 Clinical

Several clinical outcome measures were selected for this study. These were chosen on the basis of their reliability, familiarity to the neurologic community, adaptability for use in

patients who have had a stroke, and comparability to end points used in other trials of thrombolytic therapy. The modified Rankin Scale (mRS) is an overall assessment of global handicap. In the original Rankin Scale, a score of zero indicates the absence of symptoms and a score of 5, severe disability. The modified Rankin Scale adds a score of 6 for fatal outcomes. The Glasgow Outcome Scale (GOS) is a global assessment of function.[42] A score of zero on the GOS indicates a good recovery; a score of 2 moderate disability; a score of 3 severe disability; a score of 4 survival but in a vegetative state; and a score of 5, death. It has been used in previous trials assessing outcome in hemorrhagic and ischemic stroke patients. [43][43] [43] [43] [43] [43] [43] [42] [42] [38] [36][36, 35] The National Institutes of Health Stroke Scale (NIHSS) is a 42 point scale that quantifies neurologic deficits in 11 categories. Normal function without neurologic deficit is given a score of zero.

Additionally a quality of life scale outcome measure will be utilized in this study. Quality of life scales are designed to be sensitive to changes in outcome from mild and moderate stroke undetected by other outcome measures. Important parameters not fully interrogated by conventional outcome scales can be assessed by quality of life scales, including emotion, communication, cognition, and social role function. Standard measures, such as the mRS, primarily evaluate physical aspects of stroke outcome, not addressing more relevant quality of life measures. The Stroke Impact Scale (SIS) is a validated assessment of quality of life specifically in patients with stroke. [44] [39] [37][37, 36]

All 24hr Post-Randomization (mRS, GOS, NIHSS), Day 7/Discharge (mRS, GOS, NIHSS), Day 30 (mRS, GOS, NIHSS), and Day 90 (mRS, GOS, NIHSS, SIS) clinical outcome measures will be assessed by a dedicated, pre-specified Blinded Study Stroke team member with NIHSS certification and expertise with a back up person named for cases in which the blinded team member was involved in the case during the acute hospitalization. Nursing staff, patients, and their family members will be instructed not to unblind the investigators performing these assessments.

5.9.2 Angiographic

All angiograms will be assessed by a central core lab neuroradiologist who is blinded to treatment assignment and clinical status. The extent of angiographic reperfusion after treatment will be classified in the primary analysis according to Thrombolysis in Myocardial Infarction (TIMI) grades.[37,38,40, 44,45] Recanalization is graded according to the TIMI scale shown in Table 3 above. A TIMI Score will be recorded for all affected vessel segments. Additionally, mTICI classification will also be documented.

5.9.2.1 Neuroimaging Outcome Measures

- **Ischemic Core Lesion Volumes**

The initial ischemic core lesion volume will be defined using the model equations noted above respectively for MRI and CT. Final infarct volume will be defined as hyperintense regions on the day 7 FLAIR sequence (or hypodense region on day 7

CT). Lesion volumes will be quantified employing an interactive semi-automated program. For each patient, “percent lesion change” will be defined as:

$$\frac{(\text{Day 7 Final Infarct Volume} - \text{Pretreatment Core Lesion Volume})}{\text{Day 7 Final Infarct Volume}} \times 100$$

- **Perfusion Lesion Volume**

Regions of abnormal perfusion will be identified by visual inspection and outlined by hand using an interactive semi-automated image analysis program.

- **Percent Salvaged Penumbra Tissue**

The percent salvaged tissue will be defined as:

$$\frac{\text{Number of Penumbra Voxels on Pretreatment Imaging Not Designated as Final Infarct Abnormality on D7}}{\text{X 100}}$$

- **Hemorrhagic Transformation**

Hypointense regions consistent with acute hemorrhage will be identified by visual inspection on the noncontrast CT or GRE sequences and outlined by hand to provide lesion volumes. Regions of hemorrhagic transformation will be categorized as petechial hemorrhage or hematoma according to the Berger classification scheme:

HI (hemorrhagic infarction)	
Type 1:	Small petechiae along the margins of the infarct
Type 2:	More confluent petechiae within the infarcted area, but without space-occupying effect

PH (parenchymal hemorrhage)	
Type 1:	Hematoma < 30% of the infarcted area with some slight space-occupying effect
Type 2:	Dense hematoma >30% of the infarcted area with substantial space-occupying effect, or as any hemorrhagic lesion outside of the infarcted area

- **Vessel Stenosis or Occlusions**

For the pretreatment studies, the intracranial vessels will be evaluated for the presence of flow voids or signal loss suggestive of vessel occlusions or stenoses. The lesion location and severity of narrowing will be recorded for each abnormality. CTA or MRA will be considered positive for stenosis of a major vessel (ICA, MCA, ACA, PCA, basilar, vertebral) if the measured percent stenosis is $\geq 67\%$ or if a flow gap is present. Percent stenosis will be measured using WASID trial criteria adapted for the intracranial circulation from the NASCET method:

$$\% \text{ stenosis} = \left(1 - \frac{D_{\text{stenosis}}}{D_{\text{normal}}} \right) \times 100$$

(Selecting D_{normal} : distal for ICA; proximal for intracranial vessels)

